# 4.3 Study Subjects

#### 4.3.1 Disposition of Subjects

Subject disposition will be summarized for all randomized subjects by treatment group and over all subjects combined, separately for the Double-Blind Treatment Period and Open-Label Extension Period. Summaries will include the number and percentage of subjects in each analysis set, completing treatment within each study treatment period, completing the study, and the reason for discontinuation from each treatment period and the overall study. Subject disposition during the Double-Blind Treatment Period will also be summarized separately for each study site for all randomized subjects.

The number and percentage of subjects randomized by geographic region, country and site will be presented by treatment group and over all randomized subjects in the Double-Blind Treatment Period.

The number and percentage of screen failures will be presented by screen failure reason, based on the total number of subjects screened.

#### 4.3.2 Protocol Deviations

Important Protocol Deviations (IPDs) will be summarized by treatment group and over all subjects combined for the Full Analysis Set. Important Protocol Deviations are identified by the Sponsor and are defined in the ICH guideline *Structure and Content of Clinical Study Reports – Questions and Answers (E3[R1], 2013)* as a subset of protocol deviations that might significantly affect the completeness, accuracy, and/or reliability of the study data or that might significantly affect a subject's rights, safety, or well-being.

All IPDs will be determined and appropriately categorized prior to database lock and prior to breaking the blind of the treatment group assignments. The number and percentage of subjects with any IPDs as well as the number and percentage of subjects with IPDs within each category will be presented. A listing of important protocol deviations will be provided.

# 4.4 Efficacy and Pharmacodynamic Evaluation

#### 4.4.1 Datasets Analyzed

All efficacy and PD summaries will be based on the Full Analysis Set; select efficacy summaries will also be produced on the Per Protocol Set. In general, the Double-Blind Treatment Period summaries will summarize subjects by treatment group; the Open-Label Extension Period will summarize subjects by randomized treatment from the Double-Blind Treatment Period as well as by all subjects combined. A data listing of subjects excluded from the Full Analysis Set or Per Protocol Set, to include the reason for exclusion, will be presented. The efficacy and PD endpoints will be further evaluated during the Open-Label Extension Period with descriptive statistics for the Open-Label Extension Analysis Set; summaries of change over time will evaluate both change from baseline and change from the initiation of OLE.

# 4.4.2 Demographic and Other Baseline Characteristics

Demographic variables including age, sex, ethnicity and race will be summarized by treatment group and over all subjects combined for the Safety Analysis Set, Full Analysis Set, Per Protocol Set, PK Set, and the Open-Label Extension Analysis Set. Demographics will be also analyzed by the stratum factor, cholestatic liver disease type.

Age will be summarized using descriptive statistics. Sex, ethnicity, and race will be summarized with the number and percentage of subjects in each parameter category. Age, ethnicity and race will also be presented in the subgroup categories described in Section 4.4.7.8 with the number and percentage of subjects in each subgroup category.

Baseline characteristics include medical history, itch history, disease characteristics, transient elastography (FibroScan TE), estimated glomerular filtration rate (eGFR) height, weight, and body mass index (BMI). Body mass index will be calculated as: weight (kg) / [height (cm) / 100]. Baseline characteristics will be summarized for the Full Analysis Set by treatment group and over all subjects combined. Height, weight, BMI, Fibroscan, and eGFR at baseline will be summarized using descriptive statistics. Baseline eGFR will also be presented categorically by the subgroups ( $<90 \text{ vs} \ge 90 \text{ mL/min/}1.73 \text{ m}^2$ ) described in Section 4.4.7.8 with the number and percentage of subjects in each subgroup summarized.

Baseline disease characteristics to be summarized include time since initial cholestatic disease diagnosis, type of cholestatic disease, presence of inflammatory bowel disease (IBD), type of IBD, use of obeticholic acid (OCA), and use of UDCA at baseline. Time since initial cholestatic disease diagnosis (in years) is calculated as the informed consent date – the date of diagnosis divided by 365.25. Time since initial cholestatic disease diagnosis will be summarized using descriptive statistics. Type of cholestatic disease, presence and type of IBD, baseline/concurrent OCA and baseline/concurrent UDCA use will be summarized with the number and percentage of subjects in each parameter category.

Itch history will be summarized for the Full Analysis Set with the number and percentage of subjects in each parameter category of the following itch history questions:

- Did the subject have significant itch or periods of consistent itch prior to liver disease diagnosis? (Yes / No)
- Is the itch worse during the: Day / Night / No Difference
- Itch Frequency (Daily / Near-Daily / Other)
- Does Itch Interfere with Sleep (Yes / No)
- Areas of Body that are Itchy (Face / Chest / Abdomen / Back / Limbs / Palms / Soles / Scalp / Other Body Area)
- Secondary Lesions Present (Yes / No)
- Itch More Prominent in Different Seasons (Yes / No)
- Season(s) Where Itch is Worse (Winter / Spring / Summer / Autumn)
- Circumstances that Aggravate Itching (Heat / Cold / Stress / Eating / Physical Activity / Showering / Clothing / Menstrual Period / Other)
- Subject Tried Treatment in the Past? (Yes / No)
- Did Past Treatment Help? (Yes / No)

Baseline height, weight, BMI, Fibroscan, eGFR, disease characteristics, and itch history summarizations will be repeated for the Safety Analysis Set, Per Protocol Set, PK Set,

and for the Open-Label Extension Analysis Set. Baseline characteristics of height, weight, BMI, Fibroscan, eGFR, and disease characteristics will be also analyzed by the stratum factor, cholestatic liver disease type.

Medical history conditions will be mapped to preferred terms and system organ classes using MedDRA, version 25.0. Frequency counts and percentages to summarize subjects reporting abnormal medical history by system organ class will be presented for the Full Analysis Set.

# 4.4.3 Primary Efficacy Endpoint Analysis Methods

The primary estimand is the difference in means between treatment groups in the weekly WI-NRS score at Week 6 for all subjects in the Full Analysis Set. The treatment policy strategy for addressing intercurrent events will be used for the primary estimand; data collected following use of prohibited and/or rescue medications or for subjects who prematurely discontinue from study drug use will be reported in the analysis. The WI-NRS data will be analyzed using a mixed effects model for repeated measures (MMRM) based on the data from weekly scores up to Visit 6 (Week 6) in the Double-Blind Treatment Period. The model will include treatment, type of cholestatic disease (PBC, PSC), week, and treatment by week interaction as fixed effects, and the baseline WI-NRS weekly score as a covariate. The unstructured covariance model will be used. In the event the computational algorithm fails to converge, the following structures will executed: heterogeneous Toeplitz, Toeplitz, heterogeneous Autoregressive [AR(1)], AR(1), heterogeneous compound symmetry (CS), and CS. The covariance structure converging to the best fit, as determined by Akaike's information criterion (AIC), will be used. The Kenward-Roger approximation will be used to calculate the denominator degrees of freedom for the test of fixed effects. The null hypothesis to be tested is that there is no difference between EP547 and Placebo:

$$H_0$$
:  $\mu_A = \mu_B$ ;

Where  $\mu_A$  and  $\mu_B$  represent the mean values for EP547 and Placebo, respectively. The alternate hypothesis to be tested is that the treatment group means differ:

$$H_1$$
:  $\mu_A \neq \mu_B$ ;

Testing of the hypothesis is 2-sided at a 5% type I error level. Estimates of least-square (LS) means, standard error, and 95% CIs will be presented by treatment group. In addition, the LS mean difference (LSMD) of the comparison between EP547 and placebo, the standard error of the difference, and 95% CI of the difference will be presented.

Percent change from baseline will also be analyzed in the Double-Blind Treatment Period and Open-Label Extension Period. Descriptive statistics will be provided for weekly WI-NRS scores in the Double-Blind Treatment Period and Open-Label Extension Period summaries, to include the observed weekly value, change from baseline, percent change from baseline, change from initiation of OLE and percent change from initiation of OLE (in OLE-specific summaries). Initiation of the OLE is considered the Visit 6 (Week 6) average score, or the last available weekly score if Week 6 is not reported. In addition, a categorical summary of WI-NRS by itch severity (mild as defined as <4, moderate as defined as 4 to <7, and severe as defined as ≥7) will

be provided for each week. Normality assumptions will be assessed for appropriateness. If any are violated and inhibit the interpretation of the results, appropriate data transformations or non-parametric analyses will be performed in addition to other planned sensitivity analyses to support the interpretation of the treatment effect. If the model does not converge under the covariance structure testing methods, a reduced model restricted to select analysis visits (i.e., Week 1, Week 2, Week 3, and Week 6) or analysis of covariance (ANCOVA) model (with treatment group as a fixed effect and the randomization strata type of cholestatic disease [PBC, PSC] and covariate adjustment for baseline WI-NRS score) may be explored post-hoc.

# 4.4.4 Secondary Endpoint Analysis Methods

Analysis of secondary endpoints will be performed on the Full Analysis Set. Treatment group comparisons will be tested at the 5% significance level without multiplicity adjustment.

#### *4.4.4.1 5-D Itch Scale*

The change from baseline in 5-D Itch Scale total score will be analyzed using an ANCOVA model with fixed effects for treatment group and randomization strata (type of cholestatic disease [PBC, PSC]) and covariate adjustment for baseline 5-D total score. Descriptive statistics will be presented for values and changes from baseline for all post baseline visits where data was scheduled to be collected. The LS means and SE will be presented for all treatment groups. The LSMD and their SEs, 95% CIs, and p-value to test for a difference between EP547 to placebo at Week 6 will also be presented for the Double-Blind Treatment Period. Descriptive statistics will also be presented for individual component scores.

Descriptive statistics will be presented for the Open-Label Extension Period to include change from baseline and change from initiation of OLE.

# 4.4.4.2 Responder PGI-C Analysis

The proportion of subjects with improvement at Week 6 will be compared among treatment groups using a Cochran-Mantel-Haenszel (CMH) chi-square test, stratified by the type of cholestatic disease (PBC, PSC). The PGI-C responses at each visit in the Double-Blind Treatment Period (i.e., Week 6) and Open-Label Extension Period (i.e., Week 12) will also be presented with the number and percentage of subjects in each response category by treatment group along with two-sided 95% Clopper-Pearson exact CIs. Proportional endpoints (PGI-C, PGI-S and WI-NRS) will be analyzed using the number of patients in each treatment group with non-missing data at each visit (i.e., observed values) as the denominator for percentages for the Double-Blind Treatment Period and Open-Label Extension Period summaries.

[figure not shown]
# 4.4.4.3 Responder PGI-S Analysis

The PGI-S improvement in pruritus severity will be analyzed using the same statistical methodologies as the PGI-C analysis described in Section 4.4.4.2. The proportion of subjects with improvement in pruritus at Week 12 relative to their initiation of OLE value will also be summarized.

# 4.4.4.4 Responder WI-NRS Analysis

The proportion of responders in WI-NRS will be analyzed using the same statistical methodologies as the PGI-C analysis described in Section 4.4.4.2. The proportion of subjects with a reduction in WI-NRS score of  $\geq 2$ ,  $\geq 3$  and  $\geq 4$  when compared to baseline and those with WI-NRS score <4 will be assessed at each analysis visit during the Double-Blind Treatment Period and Open-Label Extension Period to include the Safety Follow-Up weeks. The proportion of subjects within each WI-NRS category will also be assessed relative to their initiation of OLE value for visits in the Open-Label Extension Period and Safety Follow-Up visits.

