### **8.1. Subject Inclusion Criteria**

To be eligible for study participation, all subjects must meet all the following inclusion criteria:

1. Age 18 to 80 years, inclusive
2. Has experienced self-reported daily or near-daily moderate to severe pruritus before Screening
3. Has a mean daily WI-NRS score indicative of moderate to severe pruritus (score  $\geq 4$ ) during Screening (Day -7 through Day -1); data from at least 4 of the 7 days are required to be considered an acceptable profile
4. If currently taking medications to treat the cholestatic disorder (including obeticholic acid [OCA]), must be on a stable dose for >12 weeks before Screening and plans to maintain the regimen throughout the study
5. If currently taking a fibrate, must be on a stable dose for >12 weeks before Screening and plans to maintain the regimen throughout the study
6. Either is not treated with or has been on a stable regimen with any medications to treat pruritus for >4 weeks before Screening and plans to maintain the regimen throughout the study
7. If female, must have a negative serum pregnancy test at Screening and be willing to not donate eggs from Screening until after the last dose of study drug and:
  - a. Is surgically sterile; or
  - b. Has been amenorrhoeic for  $\geq 1$  year without an alternative medical cause; or
  - c. If of childbearing potential, must agree to use at least 1 form of an acceptable method of contraception from Screening until the last dose of study drug. Acceptable birth control methods include:

---

 Women of childbearing potential are defined as those who are fertile, following menarche and until becoming postmenopausal unless permanently sterile. Permanent sterilization methods include hysterectomy, bilateral salpingectomy, and bilateral oophorectomy. A postmenopausal state is defined as no menses for 12 months without an alternative medical cause.

- Barrier methods of contraception (eg, male condom, female condom, cervical cap or diaphragm, and contraceptive sponge)
  - Combined (estrogen and progestogen containing) hormonal contraception associated with inhibition of ovulation
  - Progestogen only hormonal contraception
  - Intrauterine device
  - Intrauterine hormone releasing system
  - Bilateral tubal occlusion
  - Vasectomized partner

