##### **14.8.2. Analysis of Secondary and Pharmacodynamic Endpoints**

All efficacy and PD endpoints described in [Sections 14.3.2](#) and [14.3.3](#) will be summarized. Endpoints that are defined as continuous variables will be analyzed using a similar model as described for the primary efficacy endpoint if they are collected at multiple post-baseline visits; otherwise, they will be analyzed using analysis of covariance (ANCOVA) adjusted for randomization strata and baseline measurements of the response parameter of interest. Other endpoints defined as response proportions will be analyzed using a Cochran-Mantel-Haenszel test stratified by randomization strata.

Specifically for WI-NRS, data summaries will present scores, change from baseline, and response proportions by week. Percent change from baseline by week will also be summarized.

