# 4.4.7 Statistical/Analytical Issues

# 4.4.7.1 Adjustments for Covariates

The MMRM or ANCOVA model (depending on the endpoint) to compare treatment groups during Double-Blind Treatment Period will include a covariate adjustment for the baseline parameter value of interest.

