### 4.4.7.8 Examination of Subgroups

The primary efficacy endpoint and select secondary efficacy endpoints will be analyzed based on:

- Age (< 65 years of age vs  $\ge 65$  years of age)
- Gender (Male vs Female)
- Race (White vs All Other Races)
- Ethnicity (Hispanic or Latino vs Not Hispanic or Latino)
- Cholestatic liver disease type (PBC or PSC)
- Prescence of IBD (Yes or No)
- IBD Type (CD or UC)
- OCA use at baseline (Yes or No)
- Geographic region (North America vs Europe/Rest of the World)
- Baseline itch severity (moderate/WI-NRS <7 vs severe/WI-NRS ≥7)

- Any improvement in PGI-C (Week 6 for Double-Blind Treatment Period; Week 12 for Open-Label Extension Period [Open-Label Extension Analysis Set only])

The primary and select secondary efficacy endpoints to include the WI-NRS responder analysis will be analyzed for the subgroups using the Full Analysis Set and the Open-Label Extension Analysis Set. Separate summaries will be presented for each subgroup category.

Select safety analysis defined in Section 4.5.3 and 4.5.5 will be analyzed by the following subgroups:

- Cholestatic liver disease type (PBC or PSC)
- Baseline eGFR ( $<90 \text{ vs} \ge 90 \text{ mL/min/}1.73 \text{ m}^2$ )

A summary of subject disposition will also be provided by each subgroup. Demographic and baseline characteristics will be further explored by the stratum factor, cholestatic liver disease type. Summaries by subgroup will only be produced if there are at least 5 subjects in the category of interest for each treatment group. Additional subgroup analyses may be performed post-hoc, as appropriate.

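### The planned test of WI-NRS <4 is valid but omits the prognostic baseline score, and no responder endpoint gets a between-arm estimate with a confidence interval

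*SAP*

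**What the plan says.** - **Test.** SAP 4.4.4.4 covers reductions of ≥2, ≥3 and ≥4 and the status WI-NRS <4: "The proportion of responders in WI-NRS will be analyzed using the same statistical methodologies as the PGI-C analysis described in Section 4.4.4.2". SAP 4.4.4.2 gives that method as a "Cochran-Mantel-Haenszel (CMH) chi-square test, stratified by the type of cholestatic disease (PBC, PSC"). Protocol 14.8.2 agrees: "Other endpoints defined as response proportions will be analyzed using a Cochran-Mantel-Haenszel test stratified by randomization strata".
- **Estimation.** SAP 4.4.4.2 asks for Clopper-Pearson intervals by treatment group. It names no between-arm difference or interval. SAP 4.4.3 (primary) and 4.4.4.1 (5-D Itch) do ask for a between-arm difference with a 95% CI.
- **Baseline adjustment.** SAP 4.4.7.1 confines it to two model types: "The MMRM or ANCOVA model (depending on the endpoint) to compare treatment groups during Double-Blind Treatment Period will include a covariate adjustment for the baseline" value. CMH is not one of them.
- **Other use of baseline.** SAP 4.4.7.8 lists baseline itch severity (<7 against ≥7) as a subgroup and applies it here: "The primary and select secondary efficacy endpoints to include the WI-NRS responder analysis will be analyzed for the subgroups using the Full Analysis Set". Subgroup summaries are produced only with at least 5 subjects per arm in the category.
- **Missing data.** SAP 4.4.7.2 analyses responder endpoints on observed values only.

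**The concern.** WI-NRS <4 is a status, not a change. Protocol 8.1 admits any subject who "Has a mean daily WI-NRS score indicative of moderate to severe pruritus", defined as 4 or more on a scale that ends at 10. A subject who starts at 4.1 meets the endpoint with a fall of just over 0.1 points; one who starts at 9 needs a fall of more than 5. The starting score should therefore predict the outcome strongly. The ≥2, ≥3 and ≥4 thresholds differ, because baseline is part of their definition.

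Two things are at stake. An unadjusted comparison carries variance that the baseline score could remove, and a chance imbalance in baseline itch feeds straight into it. And a p-value with two separate per-arm intervals does not say how large the difference is or how uncertain it is, which is what the design of the next study needs. Protocol 5.3 says this trial is meant to guide that design.

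**Working it through.** **Inputs from the documents.** SD of change 2.5, 26 evaluable per arm, 10% withdrawal, 29 enrolled per arm (SAP 4.6); two-sided 5% (SAP 4.1.1); 1:1 allocation (SAP 3.3.3).

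**Inputs that are assumptions.** The effect is redacted in the current text. The amendment log shows 2.0 points and 80% power in superseded wording; 2.0 is used here as an assumption, with 1.5 as a check. Baseline mean, baseline SD and the slope of Week 6 on baseline are in neither document.

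**The plan's own figure first.**
- Enrolment: 26 / (1 − 0.10) = 28.9, so 29 per arm.
- Power at 2.0 points: 2.0 / (2.5 × √(2/26)) = 2.0 / 0.693 = 2.88. The normal approximation gives 82.2% and the noncentral t on 50 df gives 80.7%, consistent with the superseded 80%.
- The documents give no power or response rate for WI-NRS <4.

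**Is baseline prognostic?** In 27 simulated settings at 26 per arm (baseline mean 6-7, SD 1.2-1.7, limited to 4-10; slope 0.5-1.0; placebo change −1.5 to −2.5; effect 1.5-2.0; 25% PSC; SD of change held at 2.5), the <4 rate was 47-74% for baseline <7 and 25-60% for baseline ≥7. The gap was 13 to 33 percentage points and was present in every setting.

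**What adjustment gains.** Simulation at 26 per arm, 2,000 trials per setting, effect 2.0, baseline mean about 6.6, SD 1.5-1.8, slope 0.7-1.0:

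| Test of WI-NRS <4 | Power | Rejection under the null |
|---|---|---|
| CMH by PBC/PSC (planned) | 48-56% | 4.2-5.6% |
| Linear model with baseline | 56-60% | 4.2-5.4% |
| Logistic likelihood-ratio test with baseline | 59-63% | 5.4-6.4% |

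The linear model gains about 4 to 8 points (56 → 60 and 48 → 56) and rejects no more often than CMH under the null. The variance of the risk difference falls by about 2-9%.

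**Why the linear row is the fair comparison.** Take one stratum of N = 52 and let r be the correlation between treatment and response. CMH rejects when (N − 1)r² > 3.84, that is r² > 3.84/51 = 0.0753. A linear model without baseline rejects when 50r²/(1 − r²) > 2.009² = 4.03, that is r² > 4.03/54.03 = 0.0746. The two are nearly the same test, so the gain from the linear model with baseline comes from the baseline term.

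**Sensitivity to the effect.** Across the 27 settings, a logistic score test with baseline moved power from 47-61% to 56-66% at an effect of 2.0 (gain about 3-10 points), and from 30-40% to 37-44% at 1.5 (gain about 3-7). In the one null setting (4,000 trials) it rejected in 5.8% against 5.0% for CMH, so part of that gain is anti-conservatism. Adding the <7/≥7 split as a CMH stratum changed power by only about −1 to +5 points.

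**Chance imbalance.** In a further simulation at 26 per arm, each 1-point baseline difference between arms moved the raw <4 risk difference by 10-14 percentage points. An ordinary imbalance of one standard error (0.36-0.41 points) moves it by about 4 to 5.5.

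**The case against.** **The planned test is not wrong.** Stratifying CMH by the randomisation factor is standard, SAP and protocol agree on it, and its null rejection was close to 5% in every check. A reader might infer that the <4 comparison is biased or invalid. The documents and calculations do not support that: randomisation protects the test, and the issue is precision. This stands in full.

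**Baseline is not ignored altogether.** A reader might infer so, but SAP 4.4.7.8 prespecifies the <7/≥7 subgroup and names the WI-NRS responder analysis in it, and the primary model on the same scale adjusts for baseline. This stands. What remains is that separate subgroup summaries give no adjusted overall comparison.

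**The gain is easy to overstate.** A logistic likelihood-ratio test at the enrolled 29 per arm looks better still, and a reader might credit all of that to baseline. Two facts count against it. Responder analyses use observed cases, so about 26 per arm is the realistic number. And a likelihood-ratio test without baseline already gained about 3 points over CMH (for example 0.564 to 0.597); with the null rejection rates matched, the adjusted version gained only about 2 to 4. This stands, and it is why the claim here rests on the linear model.

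**The endpoint is minor.** It is one of seven secondary endpoints in a proof-of-concept trial, without multiplicity control or stated power. At 1.5 points it is underpowered either way. That limits the priority of the change but does not argue against making it.

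**Conclusion.** The point holds as a low-cost improvement, not as a fault in the plan. The CMH test of WI-NRS <4 is valid but leaves out a baseline score that was prognostic in every setting examined. A baseline-adjusted analysis that holds its size raises power by about 4 to 8 points, from roughly 48-56% to 56-60%. This rests on 26 evaluable per arm and SD of change 2.5, which are in the plan, and on an effect of 2.0, baseline mean about 6.6, baseline SD 1.5-1.8 and slope 0.7-1.0, which are assumed. The larger gain of the logistic likelihood-ratio test should not be quoted as the benefit, since its null rejection was about 5.4-6.4%.

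The absence of a between-arm estimate with a confidence interval needs no assumption. It follows from the text and applies to every responder endpoint.

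**What to change.** In SAP 4.4.4.4, before unblinding:

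1. For WI-NRS <4 at Week 6, specify a baseline-adjusted risk difference with a 95% CI from a model with treatment, disease type and continuous baseline weekly WI-NRS. Use a method that holds its size in small samples: a linear-probability model, or a Firth-penalised logistic model with standardisation. Check the choice by simulation.
2. Keep the CMH test stratified by disease type and report it alongside.
3. Leave the ≥2, ≥3 and ≥4 thresholds on CMH, and add the stratum-weighted risk difference with a 95% CI for each.
4. Record the change in SAP 4.7, which now reports no departures from the protocol.

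The cost is a little more analysis work and a documented departure from Protocol 14.8.2, which names CMH for response proportions. No new data are needed: the baseline weekly score is already derived for the primary model.
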